However, this new model also suffers from methodological weaknesses, (e.g. external validation without assessment of calibration, i.e. how closely the probability of the event predicted by the model agrees with the observed probability).

The current project will address the above weaknesses by exploiting the strengths of state-of theart evidence syntheses methods, in particular individual patient data (IPD) meta-analysis [20], to synthesise all the current literature on risk factors for psychosis in the ARMS group. Following this, we will develop a prognostic tool [13] to improve prediction of psychosis in the ARMS group and externally validate this is a new cohort of ARMS individuals.

3. Aims and Objectives

Aims

- To synthesise the evidence about predictive and protective factors for development of psychosis in the At Risk Mental State (ARMS) group.
- To develop a prognostic tool that predicts ARMS individuals at highest and lowest risk of psychosis that is feasible and acceptable to mental health staff and service users.
- To assess the external validity of this tool.
- To assess the health economic impact of implementing this tool in clinical practice.

Objectives

1. Evidence synthesis: To achieve this aim we will conduct a systematic review and IPD meta-analysis of prospective studies of individuals meeting ARMS criteria, including review of existing prognostic models. We will focus on risk factors for development of psychosis within the 12 months after an individual has been identified as meeting ARMS criteria. This first 12 months is the highest risk period for psychosis onset [21, 22], and the time when individuals are most distressed [23] and most likely to engage with services.

2.Development of a prognostic tool suitable for use in the NHS:

2a. Factors and models that show consistent evidence of prognostic value in the evidence synthesis phase will be discussed at focus groups with early intervention staff and service users. This is to ensure that the measures in the tool are acceptable to service users and feasible for NHS staff to conduct or arrange.

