4.3.7 Data Collection

All data will be collected by clinicians working in NHS clinical services or by a research assistant employed by the clinical teams to support data collection and extraction. Data will be anonymously transferred by the research assistant in the clinical team to the research database which contains a unique participant identifier.

Participants in the main prospective observational cohort will have the option to 'opt out' of their routinely collected data being used for the research study using a combined information sheet and opt out form.

5a) Main cohort

Baseline: CAARMS assessment will have been routinely completed by NHS clinicians, or a research assistant employed within the clinical team, to determine ARMS status at point of entry to their service. The Research Assistants within the clinical teams will conduct the brief set of non-invasive measures to inform the refined prognostic model. If the CAARMS assessment was done over 4 weeks before the additional measures, it will be repeated by the Research Assistant in the clinical team to ensure that the individual still meets ARMS criteria.

12 and **24** month follow up of routine data: All participants in the cohort will be followed up via the clinical notes at 12 and 24 months. The research assistant within the clinical team will use the clinical records to determine if transition to a first episode of psychosis has occurred. This will be informed by clinician's notes which may include the following:

- Standard diagnostic classification systems (DSM-III, DSM-IV, DSM-5, ICD-10, ICD-11) or commonly used ARMS assessment schedules (e.g. SIPS or CAARMS)
- Standard treatment pathway decisions by clinicians- i.e. moved to a first episode psychosis treatment pathway
- A treated or untreated psychotic episode of one week's duration or longer;
- Treatment with antipsychotics at dose of over 5 mg of haloperidol or equivalent for over 3 weeks

5b) Cohort subsample

Participants in the main cohort will be invited to opt in to an additional phase of the study, where they will meet with the research assistant employed by the clinical team at 12 months after they entered the clinical service, to repeat the CAARMS assessment and some additional measures as described below. If participants decide they would like to opt in, they will be given a leaflet explaining the study and complete a consent form before their assessment.

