4.3.9 Assessment of primary outcome

The primary outcome is development of psychosis by 12 month follow up. Psychosis onset will be assessed using the standard definition of psychosis included in the CAARMS. (This is essentially 7 days or more of full threshold psychotic symptoms occurring at least several times per week) or by clinician's notes on transition events which may include the following:

- Standard diagnostic classification systems (DSM-III, DSM-IV, DSM-5, ICD-10, ICD-11) or commonly used ARMS assessment schedules (e.g. SIPS or CAARMS)
- Standard treatment pathway decisions by clinicians- i.e. moved to a first episode psychosis treatment pathway
- A treated or untreated psychotic episode of one week's duration or longer;
- Treatment with antipsychotics at dose of over 5 mg of haloperidol or equivalent for over 3 weeks.

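### The subsample's 12-month interview is timed from service entry, not from the prognostic measures, so a delayed baseline shortens the prediction window for those participants

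*Protocol*

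**What the plan says.** Protocol section 4.3.7 describes three steps.

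- **Entry.** The CAARMS is done routinely "to determine ARMS status at point of entry to their service".
- **Prognostic measures.** "The Research Assistants within the clinical teams will conduct the brief set of non-invasive measures to inform the refined prognostic model". No latest date for this step is given. A recheck applies to delayed cases: "If the CAARMS assessment was done over 4 weeks before the additional measures, it will be repeated by the Research Assistant in the clinical team". Its stated purpose is to confirm that the person still meets ARMS criteria.
- **Outcome.** Subsample members have a CAARMS interview "at 12 months after they entered the clinical service". Separately, "All participants in the cohort will be followed up via the clinical notes at 12 and 24 months".

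Section 4.3.9 defines the endpoint without an origin: "The primary outcome is development of psychosis by 12 month follow up". It may be established by the CAARMS definition or from clinicians' notes. Objective 1 in section 3 sets the Phase 1 horizon as "within the 12 months after an individual has been identified as meeting ARMS criteria". The subsample in section 4.3.7 has a minimum of 100 participants.

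**The concern.** External validation compares a 12-month risk, computed from the baseline measures, with what happened in 12 months. The two windows should start together. Here the only origin stated for a 12-month outcome assessment is service entry, while the predictors may be recorded later.

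The 4-week rule does not close the gap. It triggers a repeat CAARMS, sets no upper limit on the delay and does not move the interview. Where it applies, the repeat also acts as a selection step: someone who has become psychotic since entry no longer qualifies. The weeks between entry and the measures are then event-free by design, yet they use up part of the 12 months.

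Calibration is at stake. Section 4.3.6 calls calibration-in-the-large and calibration slope sufficient for this validation. If observed risk is counted over a shorter window than predicted risk, a correct tool appears to over-predict.

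**Working it through.** **The plan's own figures (section 4.3.6).** 798 × (1 − 0.30) = 558.6, stated as 558. 558 × 0.20 = 111.6, stated as 112. 558 × 0.18 = 100.4, stated as 100. All reproduce. The stated requirement is at least 100 events.

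**Effect of a gap.** Let g be the weeks from service entry to the measures and r the 12-month risk. The Protocol gives no distribution of g, so its values here are assumptions. With a constant hazard (also an assumption), someone event-free at week g and assessed at week 52 has observed risk

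1 − (1 − r)^((52 − g)/52).

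With r = 0.20:

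| g (weeks) | Calculation | Observed risk | O/E | Shift on logit scale |
|---|---|---|---|---|
| 0 | 1 − 0.8^(52/52) | 20.0% | 1.00 | 0 |
| 4 | 1 − 0.8^(48/52) | 18.6% | 0.93 | −0.09 |
| 8 | 1 − 0.8^(44/52) | 17.2% | 0.86 | −0.19 |
| 12 | 1 − 0.8^(40/52) | 15.8% | 0.79 | −0.29 |

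The 4-week row is the boundary at which the repeat CAARMS begins to apply.

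**Sensitivity to hazard shape.** The comparison is with a 12-month prediction dated at the measures, using an assumed Weibull hazard with shape 0.6. O/E at 4, 8 and 12 weeks is 0.96, 0.91 and 0.87 if hazard time runs from the measures. It is 0.95, 0.89 and 0.83 if hazard time runs from entry. The effect is smaller, in the same direction.

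**Case A: only the minimum subsample of 100 is affected.** Suppose all 100 have the same gap and the notes recover nothing. Events lost are 100 × (0.20 − observed risk):

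- 4 weeks: 1.4 lost, total 111.6 − 1.4 = 110.2, whole-cohort O/E 110.2/111.6 = 0.987
- 8 weeks: 2.8 lost, total 108.8, O/E 0.975
- 12 weeks: 4.2 lost, total 107.4, O/E 0.962

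Within those 100, the standard error of the logit is 1/√(100 × 0.2 × 0.8) = 0.25, so even the 12-week shift of −0.29 is only slightly more than one standard error.

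**Case B: conditional on the notes follow-up also starting at service entry.** With all 558 affected, expected events at 20% are 103.9, 96.0 and 88.0 for gaps of 4, 8 and 12 weeks. At 18% they are 93.4, 86.3 and 79.0. The standard error of the logit is then 1/√(558 × 0.2 × 0.8) = 0.106, so shifts of −0.19 and −0.29 would be visible. The Protocol does not state that this case applies.

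**The case against.** The strongest reply is that the service-entry clock times one opt-in interview and does not define the primary outcome window. Subsample members are also in the main cohort, their notes are reviewed, and notes alone can establish a transition. An onset shortly after the interview can therefore still be found. This stands, and it is why the size has to be read from Case A.

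The tool's horizon can also be read as running from identification as ARMS, which section 4.3.7 places at entry. On that reading service entry is the matching origin when the entry CAARMS is the qualifying one. When the CAARMS is repeated, however, there are two qualifying dates, and anyone who had a transition between them is screened out. The observed quantity is then risk by month 12 given no event before the measures, which is lower than unconditional 12-month risk. Under a constant hazard both readings give the same ratio. Under a front-loaded hazard they differ, and the milder figures above apply only to a prediction dated at the measures.

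Three stronger inferences are tempting but unsupported:

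- **That delays beyond 4 weeks are routine.** The rule is a contingency with no stated frequency, and subsample consent at the baseline assessment with the service is compatible with little or no gap.
- **That all time before the measures is event-free.** ARMS status is rechecked only after more than 4 weeks. For shorter gaps the window from the measures is still short, but no selection step is described.
- **That the whole cohort's observed risk is biased low and the 100-event requirement fails.** This needs Case B, and the origin of the notes follow-up is not stated.

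Finally, an exact index date is often left to the analysis plan, which is not shown. That covers the undefined origin of the notes follow-up. It does not cover the interview, because the Protocol fixes its origin and a later plan cannot move an interview already held.

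**Conclusion.** The point holds for the subsample interview. For any participant whose measures come after entry, the time from prediction to interview is under 12 months. Where the gap exceeds 4 weeks, the lost time is also event-free by selection. The direction follows from the design; the size depends on gaps the Protocol does not report.

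Under a constant hazard and 20% risk, O/E among those affected is about 0.93, 0.86 and 0.79 at 4, 8 and 12 weeks, closer to 1 with a front-loaded hazard and exactly 1 with no gap. Confined to 100 participants, the cost is about 1 to 4 events before any recovery from notes. At the planned 20% rate this leaves more than 107 events, so the 100-event requirement is not threatened by this clock. At the conservative 18% rate the plan starts with 0.4 of an event to spare (100.4), so almost any loss would take it under 100. That reflects the thin margin more than this rule. A larger shortfall is possible only if service entry is also used for the notes follow-up.

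The correction is worth making because it is cheap and must be in place before interviews are booked.

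**What to change.** Set one time zero for the main cohort and the subsample: the date on which the prognostic-tool measures are completed with a valid CAARMS. Schedule the subsample interview 12 months from that date, and count notes-based transitions over the same 12 months. Record the service-entry date as well, report the distribution of the gap, and report separately any transitions found between entry and the measures, so that the selection is visible.

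The cost is one sentence in section 4.3.7, matching wording in section 4.3.9 and one extra date field. The downside is that some interviews and notes extractions fall a few weeks later.

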4.3.8 Instruments

In addition to the baseline CAARMS assessment [12], assessments will include those that measure variables identified as potential predictors and included in the prognostic tool. The exact variables will depend on Phase 1 and Phase 2 of the study. We will only include factors that are feasible for routine use in the NHS. We will also include the EQ-5D-5L [84] and a core service use form [85] adapted from previous economic evaluations in mental health. These data will be used in the economic model.

4.3.9 Assessment of primary outcome

The primary outcome is development of psychosis by 12 month follow up. Psychosis onset will be assessed using the standard definition of psychosis included in the CAARMS. (This is essentially 7 days or more of full threshold psychotic symptoms occurring at least several times per week) or by clinician's notes on transition events which may include the following:

- Standard diagnostic classification systems (DSM-III, DSM-IV, DSM-5, ICD-10, ICD-11) or commonly used ARMS assessment schedules (e.g. SIPS or CAARMS)
- Standard treatment pathway decisions by clinicians- i.e. moved to a first episode psychosis treatment pathway
- A treated or untreated psychotic episode of one week's duration or longer;
- Treatment with antipsychotics at dose of over 5 mg of haloperidol or equivalent for over 3 weeks.

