4.1.1 IPD meta-analysis of prognostic factors

Study selection criteria: The following selection criteria will be used:

Population: Individuals meeting ARMS criteria, defined as 1) attenuated psychotic symptoms, 2) full-blown intermittent psychotic symptoms and 3) genetic/familial risk for schizophrenia in conjunction with a significant decrease in functioning and operationalised using suitable measures such as the Comprehensive Assessment of At-Risk Mental States (CAARMS) [31] or the Structured Interview for Prodromal Syndromes (SIPS) [32].

Unlike previous aggregate data meta-analyses of this research area [e.g. 33], we will not consider prospective studies that only assessed for the presence of "basic symptoms" of psychosis i.e. subtle subjective cognitive and perceptual disturbances shown to predict onset of first episode psychosis [34, 35]. Basic symptoms are in fact distinct from the ARMS criteria and are not used in the NHS.

Study design: Any prospective study (i.e. cohort studies as well as randomised controlled trials of preventive interventions) with participants meeting the above-mentioned ARMS criteria will be eligible. Studies must include at least 12-month follow-up longitudinal assessments and collected data on psychosis transition in ARMS individuals.

Outcomes: Our primary outcome will be psychosis transition at 12-month follow-up assessments defined using standard diagnostic classification systems (DSM-III, DSM-IV, DSM-5, ICD-10, ICD-11) or commonly used ARMS assessment schedules (e.g. SIPS or CAARMS). Secondary outcomes will include psychosis transition at subsequent available follow-up assessments (18-month, 24-month etc) and time to transition (time to event).

Identifying studies - information sources: Database searches will be conducted on PsychInfo, PubMed, EMBASE and CINAHL. No restriction will be placed on language of publication but the searches will be restricted to 1994 onwards, the initial year of the first prospective study using ARMS criteria [36, 37]. Database searches will be supplemented by 1) inspection of studies included in previous systematic reviews and meta-analyses of psychosis transition studies; 2) inspection of reference lists of psychosis transition studies identified through the database searches.

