4.2.2 Developing a novel prognostic model

As described above, a recent systematic review identified several prognostic models and many prognostic factors described as associated with transition to psychosis in patients with ARMS. The authors of that review highlighted the poor methodological quality of the included studies and specifically stated that future studies should more strictly adhere to current checklists and guidelines on clinical prognostic models, such as the recently published TRIPOD statement [63]. Other recommendations included using an appropriate sample size, undertaking internal and external validation, and reporting model performance.

Given the poor quality of existing prognostic models and factors within this field [41], it is likely that model updating is still going to lead to a prognostic model which demonstrates poor discrimination in particular on internal validation. Even though the IPD will help to avoid some issues such as poor reporting of missing data and categorisation of continuous prognostic factors, model updating may not be sufficient to produce a well-performing prognostic model. In that case, we will develop a

novel prognostic model using the IPD from Phase 1, which will not suffer from the specified methodological flaws so frequently seen within prognosis research as outlined above.

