4.2.2.1 Data

Given that the purpose of our model is to stratify patients at risk of transitioning to psychosis within the NHS, we will only use IPD from Phase 1 from prognostic models developed within the United Kingdom, or from countries with an equivalent healthcare system. Use of the IPD will enable standard analysis methods to be used across the IPD datasets and consistent predictor and outcome definitions [26]. The transportability of the novel model will be assessed by considering the discrimination and calibration of our model within the other IPD, obtained from outside of the UK.

We will make ensure that our dataset reports at least 10 transition events per variable (EPV)[64]. This may restrict the number of prognostic factors we can consider for inclusion in the model, but we will assess this once we have produced our list of candidate predictors and are aware of the relevant data from Phase 1.

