12 month follow up for cohort subsample: CAARMS assessment will be completed by Research Assistants at 12 month follow up for a subsample of participants (minimum of 100 participants) who consent to this part of the study at their baseline assessment with the service. The 12-month time frame has been chosen as our previous cohort studies have found that most transitions to psychosis occur during this period [5, 31]. We will also include the EQ-5D-5L [32] and a core service use form [33] adapted from previous economic evaluations in mental health. These data will be used to generate estimates to populate the decision analytic model described below.

Minimising attrition: Attrition will be minimised by offering participants reimbursement of £25 per assessment. We will ask participants for the contact details of someone (relative or friend) who might know their whereabouts if they move during the follow up period. This strategy has received ethical approval in previous studies and is effective at reducing attrition.

Additionally, we will contact participants at 6 months using a method of their choice (phone, text, email, letter etc.) to 'check in'. This will be an opportunity to check contact details are up to date and

check if the participant is still with the clinical service. We will send participants a £5 voucher to thank them for keeping in touch.

We will also apply usual good practice in trial management by continuously monitoring completion of data at all visits and identify any sites that need help in achieving and maintaining high rates of return. Weekly management supervision of Research Assistants will monitor compliance to follow-up rates and solve problems relating to attrition as they arise.

Long term follow up of routine data in future studies: Additionally, through seeking consent with subsample participants to access health records up to 5 year follow up, the long term predictive validity of the prognostic model can be assessed in the sample in future research and potentially linked to other downstream physical and mental health outcomes available via electronic record records and other routine databases. Participation in any future studies and consent to contact about future studies will be completely optional.

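### The Phase 3 validation outcome is broader than the outcome behind the Phase 2 model and is not ascertained alike in everyone, so calibration may mix a definition or ascertainment effect with model error

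*Protocol*

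**What the plan says.** **Outcome behind the model.** Protocol 4.1.1 states: "Our primary outcome will be psychosis transition at 12-month follow-up assessments defined using standard diagnostic classification systems", with the alternative "or commonly used ARMS assessment schedules (e.g. SIPS or CAARMS). Secondary outcomes will include psychosis transition at subsequent available follow-up assessments". Protocol 4.2.1 updates existing models with these data. If that is not good enough, 4.2.2 develops a "novel prognostic model using the IPD from Phase 1". Protocol 4.2.2.1 expects the pooled data to allow "standard analysis methods to be used across the IPD datasets and consistent predictor and outcome definitions", which concerns consistency among the Phase 1 datasets and not with Phase 3.

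**Outcome in the validation cohort.** Protocol 4.3.9 uses the CAARMS definition of psychosis or, as an alternative, clinicians' notes on transition. The list of what those notes may contain is open. It repeats the classification systems and schedules of 4.1.1 and adds three items: "Standard treatment pathway decisions by clinicians- i.e. moved to a first episode psychosis treatment pathway"; a psychotic episode of at least a week; and "Treatment with antipsychotics at dose of over 5 mg of haloperidol or equivalent for over 3 weeks". Protocol 4.3.7 gives the same list for the notes review.

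**Ascertainment.** Under 4.3.7 the whole cohort is followed through clinical notes. In addition, "CAARMS assessment will be completed by Research Assistants at 12 month follow up for a subsample of participants", at least 100 people who opt in.

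**Analysis.** Protocol 4.3.12 evaluates discrimination and calibration of the Phase 2 model in this cohort and adds treatments received as covariates. Protocol 4.3.6 rests the sample size on calibration-in-the-large and calibration slope, and requires at least 100 events.

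**The concern.** External validation asks whether predicted risks match observed risks for the event the model was fitted to. Here the observed event is a wider version of that event, in three respects.

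- **Added criteria.** A pathway move and antipsychotic exposure are not in 4.1.1. The antipsychotic item uses the same threshold as an exclusion criterion in 4.3.5. A participant already on such treatment at entry, but for less than the exclusion duration, could come to meet the item by continuing, without any change in mental state.
- **Uneven ascertainment.** Subsample members can become events by interview or by notes, the others by notes only. Membership is by opting in, so the difference follows a self-selected characteristic.
- **Treatment on both sides.** Protocol 4.3.11 records any treatments from the case notes and 4.3.12 enters treatments received as covariates. Antipsychotic exposure could therefore be part of the outcome and also an adjustment variable.

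Calibration-in-the-large responds directly to the observed event rate. If the criterion behind each event is not recorded, nobody can tell afterwards whether a departure reflects the tool or the outcome definition.

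**Working it through.** **1. The plan's own figures (4.3.6).** 798 × 0.70 = 558.6, given as 558. 558 / 0.70 = 797.1, rounded up to 798. 558 × 0.20 = 111.6, given as 112. 558 × 0.18 = 100.4, given as 100. All reproduce, so the point does not rest on an arithmetic error.

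**2. The definitions side by side.**

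| Criterion | 4.1.1 (model) | 4.3.9 (validation) |
|---|---|---|
| DSM or ICD classification | yes | yes |
| SIPS or CAARMS | yes | yes |
| Psychotic episode of a week or more | not listed, but close to the CAARMS threshold as 4.3.9 describes it | yes |
| Move to first-episode pathway | no | yes |
| Antipsychotic exposure above threshold | no | yes (same threshold as the 4.3.5 exclusion) |

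**3. Illustration: extra events.** The documents do not say how many people would meet only an added criterion, so this is assumed. Take a model that is exactly right for the 4.1.1 event at 20%, and let a further e of the cohort be events by an added criterion only. With an intercept-only simplification:

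- shift = logit(0.20 + e) − logit(0.20)
- standard error ≈ 1/√(558 × 0.20 × 0.80) = 1/√89.28 = 0.106
- 1.96 × 0.106 = 0.21

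| e (points) | Share of all events | Shift in log-odds | Expected/observed | Shift/SE |
|---|---|---|---|---|
| 1 | 1/21 = 5% | 0.06 | 0.95 | 0.6 |
| 2 | 2/22 = 9% | 0.12 | 0.91 | 1.1 |
| 3 | 3/23 = 13% | 0.18 | 0.87 | 1.7 |
| 5 | 5/25 = 20% | 0.29 | 0.80 | 2.7 |

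Up to 3 points the shift stays inside 1.96 standard errors. At 5 points it does not.

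**4. Illustration: missed events.** Suppose the notes find only 90% or 80% of transitions outside a subsample of 100, at a 20% rate.

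- 90%: 20 + 458 × 0.20 × 0.9 = 102.4 events, a rate of 0.184. logit(0.184) − logit(0.20) ≈ −0.11.
- 80%: 20 + 458 × 0.20 × 0.8 = 93.3 events, a rate of 0.167. The shift is ≈ −0.22.

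This is the same order of size in the opposite direction, so the net sign cannot be predicted.

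**5. Events left under the 4.1.1 definition.** If a share f of all Phase 3 events is met only by added criteria:

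| f | 112 × (1 − f) | 100 × (1 − f) |
|---|---|---|
| 5% | 106 | 95 |
| 10% | 101 | 90 |
| 20% | 90 | 80 |
| 30% | 78 | 70 |

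From 112 events, the count falls below 100 once f exceeds 12/112 = 10.7%. From 100 events, any share takes it below.

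**The case against.** The best defence is that the two outcomes largely coincide. The classification and schedule criteria appear in both, and the one-week item is near the CAARMS threshold. The tool is meant for routine NHS use, so an outcome taken from routine records is a reasonable choice. This stands: the Phase 3 event is a broadened form of the Phase 1 event. A reader might infer that the cohort tests a different event altogether, but the documents do not support that.

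Second, the list can be read as evidence that informs a judgement about transition, not as a set of criteria each sufficient alone; 4.3.7 has the research assistant determine from the records whether transition occurred. This is fair, and no section says that one item is enough. But no section says that it is not, and none says how the CAARMS and notes routes combine.

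Third, the 20% rate may already include such events, because 4.3.6 bases it on service data without naming a definition. That also stands, and the share of added-only events is pure assumption.

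A reader might go further and infer that outcome raters are unblinded and discrimination is inflated. Protocol 4.3.7 says "The Research Assistants within the clinical teams will conduct the brief set of non-invasive measures to inform the refined prognostic model", and research assistants in the clinical teams also review the notes. It does not say that one person does both or sees a tool score, and masking may be set out elsewhere. Misclassification unrelated to the score would lower the c-index. Neither inference is made here.

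**Conclusion.** The point holds in a limited form. Protocol 4.3.7 and 4.3.9 allow transition to be identified in ways that 4.1.1 does not list, one of them repeating an entry exclusion threshold, and they give an opt-in subsample a second route to an event. Calibration of the Phase 2 model may then mix a definition or ascertainment effect with model error, and the plan provides nothing to separate them.

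The size and direction are unknown. Under the stated assumptions (20% rate, 558 followed up, intercept-only approximation), 1 to 5 points of added-only events shift calibration-in-the-large by 0.06 to 0.29 against a standard error of about 0.11. Only the upper end would stand out from sampling error, and incomplete notes would pull the other way. A reader might infer that a sound model would fail validation. The documents do not support that: they give no share of added-only events and set no pass mark for calibration. The case for acting is that the change is cheap and the confusion could not be undone afterwards.

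**What to change.** - Reconcile the outcome wording in 4.1.1, 4.3.7 and 4.3.9 with the exclusion criterion in 4.3.5. Say whether each listed item is sufficient alone or only supporting evidence, and on which side the one-week item falls.
- Derive the primary validation outcome from clinical notes in the same way for all participants.
- Record for every event which criterion or criteria it met.
- Pre-specify discrimination and calibration for the full Phase 3 outcome and again restricted to the 4.1.1 definition. The restricted analysis also removes events defined by antipsychotic exposure alone, which 4.3.12 could otherwise treat as outcome and covariate together.
- Use the subsample CAARMS only to estimate how accurate the notes-based outcome is.

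**Cost.** One extra field on the abstraction form and one further analysis. The restricted analysis may have fewer than the 100 events that 4.3.6 requires (below 100 of 112 once added-only events exceed about 11%, and at any share if the total is 100). The protocol should state this, which is why the proposal is to report both outcomes and not simply to replace the broad one. The accuracy estimate will also be rough: 100 people at 20% give about 20 transitions, and they are volunteers.
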